2.12 What is the planned recruitment rate?

Our early real-world experience with fourteen sites over the past 33 months has yielded a recruitment rate of 0.4 patients/site/month. However, based on our experience with the RE-ENERGIZE trial involving over 60 participating sites, our average enrollment rate was closer to 0.3 patients/per site/month. The eligibility criteria for VICToRY are simpler (fewer exclusions) but the time window is shorter, so we will use the same estimate of 0.4 patients/site/month in developing our enrollment plans. With 40 sites around the world participating, we can enroll 16 patients/month and 486 over 2.5 years of the grant. With an additional 180 from the pilot trial, this enables us to reach the desired sample size. We will use the first 9 months of the grant to obtain regulatory and ethics approvals and site activation, and we will need the final 9 months to complete 6 months follow up; to allow for delays in reaching enrollment targets; and to perform data cleaning, analysis, and write up. The total duration of the study is 4 years (2022-2026).

2.13 Are there likely to be any problems with compliance? and 2.14 What is the likely rate of loss to follow up?

In the early experience with the pilot trial (n=15 patients), we have observed 100% compliance with delivery of study product and no patients lost to 28-day follow up. We will continue to monitor and manage compliance issues that emerge through the remaining part of the pilot trial with frequent "touch-base" calls, quality metric reports, and query management. Our experience working with these sites in the RE-ENERGIZE study, in which we observed >90%

compliance with study protocol and less than 4% lost to follow up at 6 months, increases our confidence that there will be no major issues with compliance of this protocol. Moreover, given the short-term duration of the intervention (96 hours) compared to the RE-ENERGIZE trial (3 months), we expect compliance with study medication administration to be even higher than the 90% observed in the RE-ENERGIZE trial. The RE-ENERGIZE trial can be considered as a 'pilot' for all other study procedures as they are essentially the same between the 2 studies.

2.15 How many centers will participate?

We plan to recruit 40+ sites from our existing burn research network to participate in VICToRY. Interested sites to date are from: Canada (Quebec, Ontario, and Nova Scotia); USA (Arizona, Connecticut, Iowa, Maryland, Missouri, Ohio, Texas, Washington, and possibly others); Belgium, Costa Rica, France, Germany, Italy, Mexico, Paraguay, Poland, Portugal, Singapore, Spain, Thailand, and the UK. The inclusion of so many sites from different countries will enhance the generalizability of study results.

2.16 What is the statistical and data analysis plan?

In accordance with the intent-to-treat (ITT) principle, the analysis will include all patients in the arm to which they are randomized regardless of study compliance except patients who do not receive any of the study intervention (modified ITT analysis). In addition, we will conduct a per-protocol analysis of all truly eligible patients who receive all 16 doses. All of the analysis, including reporting of participant flow and patient characteristics by arm, will be presented in accordance with the CONSORT statement. Our primary outcome (alive and PODS free at 28 days) will be compared between groups using by an adjusted relative risk estimated by a modified Poisson regression with robust standard errors clustering by site and controlling for the following baseline covariates: TBSA burn, traumatic brain injury, mechanically ventilated at baseline and injury severity score.⁸⁰ This approach will meet regulatory guidance and best practices suggesting that site and strongly predictive baseline covariates be considered for adjustment in the analysis of multicenter studies.⁸¹⁻⁸³ Binary secondary outcomes will be analyzed similarly.

Based on our substantial prior experience with this population, we expect minimal missing data for all 28-day outcomes. However, details of missing data will be provided, and for the primary outcome, we will perform a sensitivity analysis using a graphical pattern-mixture tipping-point approach demonstrating the treatment effect over the possible range of missing outcomes.^{84,85} Lengths of ICU and hospital stay will be reported by arm using the subdistribution cumulative incidence function (CIF), where death is treated as a competing risk precluding the possibility of discharge. The between-arm difference in time to live discharge will be summarized by the subdistribution hazard ratio with 95% confidence intervals and p-values estimated by the Wald test from the Cox proportional hazards model, with site as a random frailty to account for potential between-site heterogeneity and adjusting for the same baseline covariates as for the primary outcome. For this analysis, survivors will be censored at the earliest of last date known alive or 183 days after randomization. Patients who die prior to discharge will be censored after the end of the follow-up period (i.e. >183 days) to account for the competing risk of death. This will yield virtually the same results as the Fine and Gray approach treating death as a competing risk precluding discharge, except we will have incorporated ICU as a random effect. This outcome is also known as time-to-discharge-alive (TTDA). The distribution of ventilator-free days and PODS-free days up to day 28 will be compared between arms by the

empirical distribution function depicting the proportion of people (y-axis) with at least 1 through 28 free days (x-axis) by arm.

Six-month mortality will be reported by group using Kaplan-Meier curves with between-group differences summarized by the hazard ratio and corresponding 95% confidence intervals estimated from the Cox proportional hazards model with site as a random frailty and adjusting for the same baseline covariates as the primary outcome. Survival will be censored at 183 days or time last known alive for patients lost to follow-up. Six-month health-related quality of life and physical-function status will be reported for survivors only since our tools (SF-36 and Katz's ADL index) are not defined for decedents. When interpreting these outcomes, we will only consider results definitive if they are in the same direction as survival. For example, if the intervention arm had both higher survival (regardless of statistical significance) and better SF-36, then we would conclude that health-related quality of life was improved in the intervention arm compared to the control arm. For each of these outcomes we will report the mean scores by arm and estimate the mean difference between arms with 95% confidence intervals. Estimates for these outcomes will be obtained from a linear mixed effects model with our primary predictor of interest being a fixed effect indicator for treatment arm but also including site as a random effect and the following fixed baseline covariates: age, sex, ethnicity, TBSA burn, traumatic brain injury, mechanically ventilated at baseline and injury severity. These estimates will use the augmented inverse probability to minimize bias due to missing data among survivors.⁸⁶

Although the secondary outcomes will play a mostly supportive and exploratory role, result interpretation will consider the multiplicity of tests, and the false discovery rate for correlated tests will be reported if nominal p-values reach ≤ 0.05 for any secondary outcomes.⁸⁷ Tertiary outcomes will be reported without p-values.

There will be two interim analyses for futility/harm after the primary outcome is available on 222 and 444 patients. Both interim analyses will suggest stopping for futility/harm if the adjusted RR of the PODS+death is >1.1 favoring control. The study will not stop early for benefit. Details of the operating characteristics of this study under this futility rule are provided in Appendix C.

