Since the solution containing vitamin C is acidic and contains sodium, acid-base and electrolyte imbalances are theoretically possible,⁷² but its effect on blood pH has been called “negligible” in patients receiving up to 8 g/m².⁷³ and metabolic acidosis has been reported in single-cases when multiple factors such as exsiccosis, acute kidney injury and other metabolic derangements occur simultaneously.^{74,75} Lastly, vitamin C may be associated with hemolysis in patients with glucose-6-phosphate dehydrogenase (G6PD) deficiency, who will therefore be excluded from participating in the trial. However, since the prevalence of G6PD deficiency is low in most if not all participating centers and since the trial is designed to facilitate early

administration to maximize benefit, we will not screen eligible patients for G6PD deficiency. Of note, most existing trials of intravenous vitamin C for sepsis have not screened for G6PD deficiency; no related adverse event has been reported thus far.⁴⁹ Hemolysis will be monitored and recorded in the case report form. If hemolysis happens during the intervention period, we will stop the study drug and provide standard supportive care (e.g. monitoring of hemoglobin, red blood cell transfusion as needed). Drug-induced hemolysis resolved when the causative drug is stopped.

Since no drug interactions have been reported in the previous studies on vitamin C used for the treatment of septic patients, we do not anticipate any drug interactions.

How will safety concerns be handled?

- 1) We will exclude patients with known G6PD deficiency.
- 2) For individual subjects, the treating physician will have the right to discontinue study product if the enrolled patient develops a new diagnosis of oxalate kidney stones, severe hemolysis, severe acid-base/ electrolyte imbalances or refractory hypoglycemia or any other medical complication such as an SAE that, in the opinion of the treating physician, ongoing use of study product would compromise patient safety.

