2.2 What are the planned trial interventions?

Patients will be allocated to 2 groups: **Vitamin C group:** patients will receive intravenous vitamin C at 50 mg/kg every 6 hrs for 96 hours. **Control group:** patients will receive a similar

amount of placebo (either D5W or saline) delivered in the same manner as the vitamin C. The vitamin C will be sourced locally and prepared in a blinded manner by local research pharmacies. The vitamin C will be diluted in either 0.9% NaCl or D5W to a concentration of ≤ 92 mg/mL. According to stability testing, vitamin C concentration between 36 and 92 mg/mL, diluted in either normal saline or D5W, and stored protected from light at 2-8°C is physically and chemically stable for at least 14 days.⁷⁶ The volume for dilution will be determined based on the patient's pre-burn dry weight to a maximum of 150 kg. Dosing will be calculated based on a weight of 150 kg for patients weighing ≥ 150 kg. The duration of each infusion will be dependent on infusion rate. The infusion rate will not exceed 100 mg/min. Below is a sample table of infusion volumes and durations based on patients with a pre-burn dry weight between 50 and 175 kg, dosed at a maximum of 150 kg:

	Kg	mg	mg	mL	Minutes
Pre-Burn Dry Weight	Dosing Weight	mg/day based on highest dose (200 mg/kg)	mg/dose (q6h)	Volume/dose (max dose of 92mg/mL)	Duration of infusion (max rate of 100mg/min)
50 kg	50	10000	2500	27	25
75 kg	75	15000	3750	41	37.5
100 kg	100	20000	5000	54	50
125 kg	125	25000	6250	68	62.5
150 kg	150	30000	7500	82	75
175 kg	150	30000	7500	82	75

A missed dose administration will be compensated by a make-up dose within 24 hours of the missed dose. Open-label vitamin C to a maximum of 200 mg/day delivered intravenously or 1,500 mg/day enterally will be allowed in study subjects for the purpose of nutrient repletion. There are no excluded medication treatments before or during the trial other than high dose IV vitamin C. There is no 'rescue' medication for study subjects.

We will provide an inventory Drug Accountability Log (DAL) which will be maintained by the unblinded pharmacist at each participating site to document receipt, distribution, and destruction of the locally sourced IV vitamin C. A participant specific DAL will also be provided for each pharmacy team member to record all doses of study product, active or placebo, prepared and administered to each participant.

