2.6 What is the proposed duration of treatment period?

96 hours based on [name] trials demonstrating safety and efficacy of this duration. Shorter dosing intervals have demonstrated a reoccurrence of hypovitaminosis after stopping the study intervention.^{25,57}

If a study patient is prematurely withdrawn from the trial (see safety criteria in section 1.5), the timing and reason for the withdrawal from vitamin C administration will be noted and complete study outcomes will continue to be collected. Patients withdrawn from vitamin C/placebo administration will be followed up for 3 days after last administration of the investigational product. If patients withdraw from the entire study, the collected study data will be kept to ensure safety, but no further data will be collected. As we expect this event to be rare, we will not replace such subjects.

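### The all-16-dose per-protocol set drops patients who die or are stopped for safety before dose 16, so its relative risk can be biased either way if that early loss differs between arms

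*Combined protocol and SAP*

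**What the plan says.** Section 2.16 of the combined protocol and SAP names two analysis sets. The main one keeps patients in their randomized arm "regardless of study compliance except patients who do not receive any of the study intervention (modified ITT analysis"). The second is supplementary: "we will conduct a per-protocol analysis of all truly eligible patients who receive all 16 doses".

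Section 2.2 sets the course: "patients will receive intravenous vitamin C at 50 mg/kg every 6 hrs for 96 hours". It also provides for gaps: "A missed dose administration will be compensated by a make-up dose within 24 hours of the missed dose". Section 2.16 does not say whether a make-up dose counts toward the 16.

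Section 1.5 provides for stopping early. On individual safety grounds "the treating physician will have the right to discontinue study product if the enrolled patient develops" one of several listed complications, or another complication such as a serious adverse event. For hemolysis it says: "If hemolysis happens during the intervention period, we will stop the study drug". For patients taken off study drug, section 2.6 states that "complete study outcomes will continue to be collected".

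The primary outcome (sections 2.8 and 2.9) is persistent organ dysfunction or death at 28 days (POD+death). The plan gives no rule for interpreting the per-protocol result.

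**The concern.** To enter the per-protocol set a patient must be alive and still on study drug when dose 16 is given. Both conditions arise after randomization. The first overlaps with the endpoint, because an early death is an event. The second depends on how the patient tolerated the infusion. A patient whose drug was stopped exactly as section 1.5 allows therefore leaves the set called per-protocol, although the protocol was followed and the 28-day outcome is known.

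If vitamin C caused early deaths, or stops among patients with poor prognosis, those patients would leave mainly the vitamin C arm and the per-protocol RR would look better than the mITT RR. If vitamin C prevented early deaths, the same rule would understate benefit. What is at stake is how a disagreement between the two analyses would be read. Section 1.3 reports RR 1.21 on this composite at the same dose in septic shock (adjusted RR 1.15, 95% CI 0.98 to 1.46, with no significant rise in mortality). A per-protocol RR near 1 could then be set against an adverse mITT RR, and the plan does not say which prevails.

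**Working it through.** **The plan's own figures.** 96 h / 6 h = 16 doses, so 16 is the complete course. With dose 1 at hour 0, dose 16 is due at 15 × 6 = hour 90. A death or stop after dose 16 stays in the set; make-up doses could push completion later.

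Section 2.10 states 78% power for 27% vs 18% with 333 per arm. On the log-RR scale, SE = √(0.73/(333 × 0.27) + 0.82/(333 × 0.18)) = 0.148, and power = Φ(ln 1.5/0.148 − 1.96) = 78.4% without interim looks. A simulation of 200,000 trials with the RR > 1.1 rule gives 78.6%. The stated figure is reproduced, and it does not involve the per-protocol set.

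**Simple illustration.** Let p be an arm's 28-day event risk and e the share that dies or is stopped before dose 16. If all of those are events, the risk among completers is (p − e)/(1 − e). The 27% control risk is from section 2.10; every e, and each vitamin C risk, is an assumption.

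- Placebo: (0.27 − 0.04)/0.96 = 0.2396.
- Vitamin C with 3 more points of early events: (0.30 − 0.07)/0.93 = 0.2473. Per-protocol RR 1.03; with everyone kept, 0.30/0.27 = 1.11.
- Vitamin C with 4 more points: (0.31 − 0.08)/0.92 = 0.2500. Per-protocol RR 1.04; with everyone kept, 0.31/0.27 = 1.15.

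This is a severe case: every early-loss patient is an event, and all the excess events fall in the group removed.

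**Wider range.** Separate early deaths (d) from safety stops (s), and let stopped patients have event risk r. Fix the placebo risk at 0.27 and give completers the same risk q in both arms, so the 16-dose RR is 1.00 by construction:

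q = (0.27 − d₀ − s₀r)/(1 − d₀ − s₀)

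RR with everyone kept = [d₁ + s₁r + (1 − d₁ − s₁)q]/0.27

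| Assumed, placebo vs vitamin C | RR, everyone kept | RR, 16-dose set |
|---|---|---|
| Deaths 2% vs 2%, no stops | 1.00 | 1.00 |
| Deaths 2% vs 2%, stops 1% vs 5%, r = 0.27 | 1.00 | 1.00 |
| Deaths 2% vs 2%, stops 1% vs 5%, r = 0.60 | 1.05 | 1.00 |
| Deaths 2% vs 4%, 5% or 6%, no stops | 1.06, 1.08, 1.11 | 1.00 |
| Deaths 2% vs 4%, stops 1% vs 5%, r = 0.60 | 1.11 | 1.00 |
| Deaths 3% vs 6%, stops 1% vs 5%, r = 0.60 | 1.14 | 1.00 |
| Deaths 4% vs 2%, no stops | 0.94 | 1.00 |

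Worked example, last row: q = 0.23/0.96 = 0.2396, and (0.02 + 0.98 × 0.2396)/0.27 = 0.94. Here the 16-dose set misses a benefit.

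If completers have a true RR of 0.80 and early deaths are 2% vs 4% to 6%, the RR with everyone kept is 0.87 to 0.93 against 0.80 in the 16-dose set. With equal deaths of 2% the former is (0.02 + 0.98 × 0.80 × 0.2551)/0.27 = 0.81. That 0.01 gap is dilution by deaths common to both arms, not selection.

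**The case against.** The strongest reply is that nothing important depends on this analysis. It is an addition to mITT, has no alpha and no stated decision role, and is absent from the power calculation and from Table B. The interim harm rule does not name its analysis set, but nothing ties it to the per-protocol set. That stands, and it limits the weight of the point.

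A reader might infer that the 16-dose rule hides early harm in the trial. The documents do not support that. mITT retains everyone who received any study product, outcomes are still collected after stopping, Appendix B records related events that lead to early stopping, and under section 1.5 the data monitoring committee reviews serious adverse events and, by group, events of interest, kidney injury and renal replacement therapy. A patient who dies after one dose counts in the main result.

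It is also fair to say that early loss may be small. Patients not expected to survive 72 hours are excluded, section 2.10 assumes no more than 10% dead by day 47, and section 2.13 reports full delivery in the first 15 pilot patients. But the entry criterion is a prognosis that cannot rule out deaths or stops before hour 90, and 15 patients say little about rates of a few percent.

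Finally, one can argue that a full-course completer set is a familiar definition and the choice is a matter of taste. That does not stand: followed exactly, the rule can return a per-protocol RR distorted by selection, and the plan has no safeguard against it.

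**Conclusion.** The point holds for the supplementary per-protocol analysis only. As defined, the set selects on survival and tolerance up to dose 16. Its RR is distorted if early death or stopping differs between arms in frequency or prognosis. Neither bias as such nor its direction is given: a reader might infer that it always favours vitamin C, but the error reverses if the drug reduces early deaths, and it vanishes when loss is equal and prognostically similar.

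In the assumed cases the gap runs from none to about 0.14 on the RR scale. The larger gaps need early deaths to differ by several percentage points, or stopped patients to fare much worse than average. The documents give no rate of death or stopping before dose 16, so these figures show sensitivity and are not a forecast. The main analysis and the power calculation are unaffected. The definition should still be changed, because a per-protocol result with no rule for reading it could be used to soften an adverse mITT finding.

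**What to change.** In section 2.16, define per-protocol adherence on doses due: truly eligible patients who received every dose falling due, counting permitted make-up doses, until death, discharge or a safety stop under section 1.5. Keep those patients in the set and count their 28-day outcomes. Report exclusions by arm and reason. Show 16-dose completers in a descriptive table only, without a treatment comparison. State that the per-protocol analysis supports mITT and does not override it.

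The cost is SAP wording. Dose times, stop reasons and outcomes after stopping are already to be collected (section 2.6 and Appendix B), and neither the sample size nor patient management changes. The downside is small: adherence on doses due is still judged after randomization, and the result may lie close to mITT. In the scenarios above it would equal the RR with everyone kept, because the only losses assumed there are early deaths and safety stops.

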Appendix B: Schedule of Assessments

SCHEDULE OF ASSESSMENTS	Screening / Baseline Day 1	Day 2	Day 3	Day 4	Day 5	Day 6	Day 7	Day 8	Ad Hoc	Outcomes (d/c to 90 days max)	6 Month Follow-Up	Early withdrawal
SCREENING/Pre-RANDOMIZATION (collected once)												
Obtain Consent												
Rule-out Pregnancy (if applicable) as SOC												
Inclusion Criteria met (age; burn size)												
Exclusion Criteria - none present												
BASELINE (collected once at beginning of study period)												
Randomization												
Demographics, Comorbidities, APACHE II Score, hospital & ACU admit date/time												
Burn Injury Assessment (date/time; type; % TBSA)												
Clinical Frailty Scale assessment												
TRAUMA (collected once at baseline)												
Traumatic Brain Injury, GCS, other trauma												
SOFA (record from ACU admission to 3 days after last dose of IP)												
PaO ₂ /FiO ₂ (lowest)												
Platelets (lowest)												
MAP (lowest)												
MICROBIOLOGY (record from >72 hours after ACU admission to ACU discharge for a maximum of 3 months)												
Gram negative bacteremias												
VENTILATION/RRT (record data from hospital admission to hospital discharge for a maximum of 3 months)												
Invasive Mechanical Ventilation												
Renal Replacement Therapy (dialysis)												

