Appendix C: Interim Analysis and Sample Size Consideration

We plan to conduct formal interim analyses once 28-day PODS+death is available for one-third ($n=222$) and two-thirds ($n=444$) of the full study ($n=666$). Given the conflicting literature with regards to the direction a vitamin C effect, we plan for one-sided interim analyses which would suggest stopping for harm/futility if a signal increased PODS+death is observed in the vitamin C arm. We have examined the study characteristics of various stopping rules using 10,000 simulations for each treatment effect scenario. A relative risk (RR) of 1 equates to the null hypothesis, an $RR < 1$ favours Vitamin C, and in all scenarios, we assume a 27% 28-day PODS+death rate in the control arm. With 10,000 simulations, the estimates of all percentages will have at least a 95% chance of being estimated to within 1% and the mean RR and Bias have more than a 95% chance of being accurate to the second (and final) decimal reported. All simulations were analyzed according to the analysis plan by using modified Poisson regression clustering for site and controlling for: age, sex, ethnicity, TBSA burn, traumatic brain injury, mechanically ventilated at baseline and injury severity. However, the data generated assumed that each observation was independent, so that there was no clustering by site and none of the covariates were related to the outcome. It may be noted that the actual number of simulations is up to 0.7% less than 10,000. This is due to the generalized estimating equations (GEE) algorithm used for the modified Poisson model not converging. We chose the modified Poisson over the log-binomial model because the log-binomial model did not converge in over 30% of the simulations and we chose modified Poisson over logistic regression due to the preference of estimating relative risks rather than odds ratio.

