We wanted to have a high probability of stopping at the interim if vitamin C was harmful, but a low probability of stopping if vitamin C was not harmful. We also wanted the stopping rule to cause minimal type I error inflation, minimal loss of power and minimal bias in the final estimate – which would come from the interim analysis if the study stopped early. Finally, we could not choose a rule that would guide the DMC to recommending continuing the study at an uncomfortably large RR. Based on these criteria and simulation results, we choose a stopping threshold of $RR > 1.1$ (in the direction of harm) regardless of statistical significance at either of two interim analyses. This stopping rule only trivially reduced power for detecting benefit of vitamin C and did not meaningfully increase the type I error compared to no interim analysis. The simulation results with this stopping rule are presented in table B. Under the null hypothesis, the $RR > 1.1$ stopping rule would have a 33.3% and 8% chance of stopping at the first and second interim respectively. The expected RR would be 1.08 (a bias of 0.08), but the 95% confidence intervals would contain the true value of one 94% of the time which is the same as obtained without a stopping rule. The trivial type I error inflation and corresponding sub-nominal 95% confidence interval coverage appears even without an interim analysis due to using the modified Poisson approach which uses robust standard errors. With the $RR > 1.1$ rule, if the true $RR=1.2$ there will be a 67% chance of stopping at the first interim, and a 14% chance of stopping at the 2nd interim. With a true $RR=1.333$ there would be an 83% and an 11% chance of stopping at the 1st and 2nd interim analysis respectively. Under the assumed effect size of $RR=0.666$ we would maintain 78% power with only a 1% chance of stopping a study early that would otherwise have gone on to be statistically significant.

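### The primary model has two covariate lists, the RR > 1.1 interim rule names neither, and age is missing from the section 2.16 list; one list including age should be fixed for both interims and the final analysis.

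*Combined protocol and SAP*

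**What the plan says.** Section 2.16 compares PODS+death at 28 days by modified Poisson regression, clustered by site and "controlling for the following baseline covariates: TBSA burn, traumatic brain injury, mechanically ventilated at baseline and injury severity score". Binary secondary outcomes are handled in the same way. Time to discharge alive and six-month mortality take over the primary outcome's covariates.

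Appendix C describes the simulations behind the power and the stopping rule, and claims to follow the plan: "All simulations were analyzed according to the analysis plan by using modified Poisson regression clustering for site". The covariates it names for that model are nevertheless different: "controlling for: age, sex, ethnicity, TBSA burn, traumatic brain injury, mechanically ventilated at baseline and injury severity". That is seven covariates against four; the additions are age, sex and ethnicity. Within section 2.16 the same seven appear only in the six-month quality-of-life and function models. Appendix C also states that in the generated data "there was no clustering by site and none of the covariates were related to the outcome".

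The interim rule in section 2.16 reads: "Both interim analyses will suggest stopping for futility/harm if the adjusted RR of the PODS+death is >1.1 favoring control". No covariate list is attached. Appendix C adds that the threshold applies "regardless of statistical significance at either of two interim analyses".

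Appendix B's baseline rows include "Demographics, Comorbidities, APACHE II Score, hospital & ACU admit date/time", and its trauma row covers traumatic brain injury, GCS and other trauma. No row names an injury severity score.

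**The concern.** Both lists are current text and both claim to describe the primary model. The seven-covariate list matches the quality-of-life model. A reader therefore cannot tell whether section 2.16 left three covariates out on purpose or Appendix C took its list from the wrong model.

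The choice matters most at the interims. The rule compares a point estimate with a fixed cut and makes no allowance for uncertainty, so a small shift from a different model can move the estimate across 1.1. Appendix C says that if the trial stops early the final estimate comes from the interim, so the list would then also determine the reported RR. An unsettled list is a choice that could be made with data in view.

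Two smaller matters follow. Section 2.16 justifies adjustment by appeal to strongly predictive baseline covariates. Age is the first planned subgroup factor, is in the quality-of-life model and in Appendix C, and falls under the demographics already collected, yet its omission from the primary model is not explained. Also, one of the four named covariates is not defined: the primary-model text calls it a score, while the quality-of-life text and Appendix C say only injury severity.

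**Working it through.** **Inputs from the plan.** Control rate 27%, treated rate 18%, 333 per arm, two-sided alpha 0.05 (section 2.10). Interims at 222 and 444 patients, threshold RR 1.1 (section 2.16, Appendix C). Table B: power 78.1%; null stopping 33.3% and 8.0%.

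**Inputs not in the plan.** The documents do not say how strongly age or TBSA predicts PODS+death. The odds ratios (OR) per SD used below are assumptions, shown as a range.

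**1. Reproduce the power.** SE(log RR) = √[(1−p₁)/(n·p₁) + (1−p₀)/(n·p₀)] = √[0.82/59.94 + 0.73/89.91] = √(0.01368 + 0.00812) = 0.14765. Power = Φ(0.40547/0.14765 − 1.960) = Φ(0.786) = 78.4%. The two-proportion formula gives 79.6%. Both agree with the stated 78%.

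**2. Reproduce the first-look stopping probability.** With 111 per arm and RR 1, SE = √(2 × 0.73/29.97) = 0.2207. P(RR > 1.1) = 1 − Φ(0.0953/0.2207) = 1 − Φ(0.432) = 33.3%, as in Table B. The same formula gives 66.2% at RR 1.2, 83.0% at RR 1.333 and 2.5% at RR 0.667. Table B has 67.4%, 82.7% and 2.7%.

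**3. Fit both lists to the same simulated trials under Appendix C's assumption.** This used modified Poisson regression, 40 sites, site-clustered robust SE, looks at 222, 444 and 666, and 3,000 trials per scenario. With no prognostic covariate, null stops were 34.5% and 7.9% with four covariates and 34.6% and 8.4% with seven. Power was 79.9% and 79.7%. The plan's operating characteristics therefore do not depend on the list.

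**4. Repeat with assumed prognostic effects.** A trial counts as discordant if one list would stop it at either interim and the other would not. The variance ratio is for log RR at n = 666, four covariates over seven. The first row of each block has TBSA OR 1; the others have TBSA OR 2 per SD.

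| True RR | Assumed age OR per SD | Discordant | Variance ratio | Power, 4 covariates | Power, 7 covariates |
|---|---|---|---|---|---|
| 1 | 1 | 3.2% | 0.997 | – | – |
| 1 | 1.5 | 7.0% | 1.024 | – | – |
| 1 | 2 | 11.0% | 1.065 | – | – |
| 1 | 3 | 15.1% | 1.146 | – | – |
| 0.667 | 1 | 0.5% | 0.995 | 79.9% | 79.7% |
| 0.667 | 1.5 | 0.9% | 1.016 | 80.7% | 81.9% |
| 0.667 | 2 | 1.7% | 1.053 | 80.8% | 82.9% |
| 0.667 | 3 | 1.6% | 1.041 | 79.9% | 83.0% |

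Monte Carlo SE is about √(0.8 × 0.2/3000) = 0.7 points on power and √(0.032 × 0.968/3000) = 0.3 points on the 3.2%. The variance ratios are noisy too: for OR 3 they are 1.146 at the null and 1.041 at RR 0.667.

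**5. A second simulation and a hand check.** A logistic outcome model with age log-odds of 0.3, 0.5 and 0.7 per SD (OR 1.35, 1.65, 2.01) and true RR 1.0–1.2 gave per-look discordance of 5.6–11.6% at n = 222 and 3.8–10.1% at n = 444. The SD of the difference between the two RRs at n = 222 was 0.05–0.09. As a check, discordance ≈ E|D| × the density of log RR at log 1.1. That density under the null is 0.3634/0.2207 = 1.647. Dividing the SD by 1.1 to reach the log scale and using E|D| = 0.798 × SD gives 0.798 × 0.0455 × 1.647 = 6.0% and 0.798 × 0.0818 × 1.647 = 10.8%, in line with the simulation.

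Adding age to TBSA and ventilation in this second model (1,500 trials per cell) moved power from 79.9%, 81.1% and 81.9% to 81.0%, 81.5% and 83.1%, gains of 1.1, 0.4 and 1.2 points. Together with the gains of 1.2, 2.1 and 3.1 points in step 4, the range is roughly 0.4–3 points.

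**The case against.** The case for leaving this as a wording matter is substantial, and much of it stands.

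- Section 2.16 is the analysis plan. It defines an adjusted RR with four covariates, and the interim rule later in the same section refers to the adjusted RR. The natural reading is that the four-covariate list governs. A reader might infer two equally authoritative primary results; the documents do not support that.
- A reader might infer that Table B or the 78% power is wrong because it was simulated with another list. It is not. Appendix C's covariates were unrelated to the outcome, and steps 1–3 recover its figures with either list.
- The rule suggests stopping and guides the monitoring committee. It does not stop the trial automatically.
- A reader might infer that precision is certainly lost. The documents give no age–outcome association. Age's subgroup rationale is vitamin C deficiency, which concerns effect modification and does not establish prognostic strength. Under Appendix C's assumption the loss is nil.
- A reader might infer that the injury severity score is not collected. Appendix B is a schedule, the case report form is not among the documents, and other trauma is recorded. What can be said is that Appendix B does not list the score.

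What remains is that Appendix C expressly claims to follow the plan while fitting a different model, that the point-estimate rule names no list, and that the severity covariate is undefined.

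**Conclusion.** The inconsistency is real and rests on the text alone. It does not invalidate the stated power or stopping probabilities. Its practical size is the chance that the stop/continue recommendation depends on the list: about 3% of null trials if no covariate is prognostic, about 7–15% if age has an assumed OR of 1.5–3 per SD with TBSA at an assumed OR of 2, and under 2% at RR 0.667. The disagreement is thus concentrated near the threshold, where the rule has to discriminate, and is slight if vitamin C works as hoped.

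Omitting age may give up some precision: none under Appendix C's assumption, roughly 0.4–3 power points under the assumed effects, and the smaller of these gains are within simulation noise. This is a supporting reason to include age, not a defect in its own right.

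I rate it as should-fix: a free improvement, because age is already collected and already in Appendix C's model.

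**What to change.** State one covariate list, word for word the same in section 2.16 and Appendix C, and say that it applies to both interim analyses and the final analysis. Include age (continuous) with TBSA, traumatic brain injury and baseline ventilation. Say explicitly whether sex and ethnicity are in or out. Define the injury severity variable, use one name for it throughout, and list it in Appendix B; otherwise name a severity score that Appendix B already lists, such as APACHE II. Outcomes that borrow the primary covariates will then follow the same list.

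Finalise this before the next unblinded look, so that the list cannot be chosen with interim results in view. The cost is a few lines of text and, if the injury severity score is kept, one row in Appendix B. Age needs no new data. Table B need not be re-run for the list alone; a re-run would add information only if the simulated covariates were also made prognostic.
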